## 2.0 BACKGROUND AND RATIONALE

Patients who are suspected of suffering from an arrhythmia-related condition typically undergo electrocardiography (ECG) monitoring. Clinical symptoms associated with arrhythmia may include palpitations, shortness of breath, dizziness, lightheadedness, pre-syncope, syncope, or anxiety. Arrhythmias may also present asymptotically. Arrhythmias often occur infrequently and may not be detected with in-clinic 12-lead ECG monitoring (which records 10 seconds of data), or traditional ambulatory monitoring (i.e., with a Holter device up to 48 hours). Long-term 14-day continuous ambulatory ECG monitoring is useful for the detection of infrequent arrhythmic events [1], though further extending the monitoring period may aid in detection of additional arrhythmias and provide additional clinical insights.

The Zio monitor (K202359) received FDA 510(k) clearance on May 21, 2021 and is a long-term continuous ambulatory patch ECG monitor which adheres to the patient's left pectoral region. Additional description of the device is provided in **Table 1**. The Zio monitor is substantially equivalent to the predicate Zio XT device but is designed to be smaller and more than 50% lighter.

The Zio monitor is breathable with a waterproof housing, and a more flexible design for a secure attachment. These refinements allow for a more comfortable wear experience [2] with longer wear times and, therefore, provide more complete diagnostic data [3].

Like the predicate Zio XT device, Zio monitor is currently indicated for long-term continuous monitoring of up to 14 days. However, successful performance verification testing at iRhythm has demonstrated that the Zio monitor is capable of recording continuous ECG data for up to 21 days.

This extended wear clinical design validation study will assess the extended wear performance of the Zio monitor device, by having participants wear the device for as long as possible (up to 30 days) following an updated skin preparation process.

The study device includes the wearable ECG adhesive assembly and symptom button common to both the Zio monitor and next generation Zio AT (Zio MCT) ambulatory cardiac monitoring devices. The gateway associated with Zio MCT necessary for transmission of ECG data during device wear will not be included as part of this study. For simplicity, the study device will be referred to Zio monitor within this protocol. Additional information regarding the study device is included in Section 2.3.

The Zio monitor device should not be submerged in water. During a bath, keep the device above water. Please refer to the Zio monitor application instructions for the full set of details.

Additionally, the percentage of analyzable ECG signal (i.e., percent analyzable time) will be assessed against a performance benchmark of 80%. The device tested in this extended wear study will be the design cleared in K202359, with minor improvements for manufacturability and with the programming configurations updated to allow for continuous ECG data recording for up to 30 days. Performance objectives include a mean wear time of at least 21 days, and percent analyzable time (i.e., artifact-free ECG signal) greater than 80% for at least 90% of study participants.

## 2.1 Name of the Device

The device to be tested is the modified Zio® monitor (iRhythm Technologies, Inc., San Francisco, CA), inventory part number DFG0001, or equivalent.

## 2.2 Intended Indication for Use

The Zio monitor is a prescription-only, single-patient-use ECG monitor that continuously records data for up to 14 days. It is indicated for use on patients who may be asymptomatic or who may suffer from transient symptoms such as palpitations, shortness of breath, dizziness, lightheadedness, pre-syncope, syncope, fatigue or anxiety.

In this extended wear clinical study, the Zio monitor is being evaluated in participants who will wear the device for up to 30 days, in order to achieve a mean wear time of greater than 21 days.

## 2.3 Description of the Device

The Zio monitor is a non-sterile, single-patient-use ECG monitor and recorder that provides a continuous, single-channel recording, and is substantially equivalent to the predicate commercial Zio XT Patch (K121319). The device is FDA cleared to be marketed commercially for recording of up to 14 days. See **“Table 1: Device Comparison”** for additional details. The predicate Zio XT device has been the subject of extensive clinical study. Findings have demonstrated improved diagnostic yield as compared to 24-48 Holter monitoring [4-7] and other ambulatory monitoring modalities [8].

The patch will be applied to the upper left pectoral region and activated by either the patient at home or in the clinic by a trained health care provider. Once activated, the Zio monitor records ECG data without patient interaction, with the goal of improving patient compliance via simplicity of operation. There is a surface LED light that blinks to indicate proper activation and that the device is working or to indicate loss of connection with the skin or the presence of error conditions.

When applied, the device provides continuous, single-channel ECG recording into memory without patient interaction for the duration of the prescribed monitoring. The Zio monitor features an embedded real-time clock (RTC) for reporting purposes. The RTC is initialized at the manufacturing facility and requires no patient or user interaction. ECG data are acquired via electrodes mounted on the underside – the skin contact side – of the patch. Data are sampled with an analog/digital converter (ADC), and subsequently saved to the onboard memory. Stored ECG data are recorded into non-volatile memory, so data will not be lost in the event of power supply failure or battery expiry.

There is a button on the surface of the patch, which may be pressed by the patient to indicate when he or she is experiencing a symptom. This button press is logged by software into a secondary data stream, where event time is noted. Recording continues without interruption.

During normal operation, the device dynamically adjusts the input signal gain to a level that will maximize usage of ADC dynamic range and improve digital resolution of the recorded ECG signal, thereby improving the fidelity and contributing to improved interpretation results, particularly in situations of low-amplitude input signals.

At the conclusion of the wear period, the Study Staff or participant will remove the patch using the supplied materials and return it to the Sponsor. Once received, the recorded data will be downloaded for analysis by the Sponsor. The recorded ECG data are processed for detection of arrhythmias using an FDA-cleared (K222389) set of artificial intelligence algorithms [9] combined with trained cardiac technician review to generate a preliminary report describing rhythm findings.

**Table 1: Device Comparison (Substantial Equivalence Summary)**

Feature	Predicate Commercial Device: Zio® XT Patch (K121319)	Study Device: Zio® monitor (K202359)
Indications for Use		
Indications for Use Statements	The Zio® Patch is a prescription-only, single-patient-use, continuously recording ECG monitor that can be worn up to 14 days. It is indicated for use on patients who may be asymptomatic or who may suffer from transient symptoms such as palpitations, shortness of breath, dizziness, lightheadedness, presyncope, syncope, fatigue, or anxiety.	The Zio® monitor is a prescription-only, single-patient-use ECG monitor that continuously records data for up to 14 days. It is indicated for use on patients who may be asymptomatic or who may suffer from transient symptoms such as palpitations, shortness of breath, dizziness, lightheadedness, pre-syncope, syncope, fatigue or anxiety.
General Characteristics		
Classification	Class II: 21CFR870.2800	Same
Product Code	DSH	Same
Patient Environment	Ambulatory	Same
Patient Population	Non-pediatric, non-critical care patients	Same
Programmed ECG Storage Duration	14 days	Up to 30 days
Technological Characteristics		
Event Trigger	Manually by patient	Same
Size	The Zio Monitor has a reduced form factor	
Performance Characteristics		
Weight	24.7 g	10.0 g
Dimensions	5.2 x 2.0 x 0.5 in	5.5 x 2.2 x 0.4 in
Photograph or Drawing		

Feature	Predicate Commercial Device: Zio® XT Patch (K121319)	Study Device: Zio® monitor (K202359)
	
Zio XT (K121319)
 	
Zio® monitor (K202359)
 

In addition to the Zio monitor and Zio XT long-term continuous ambulatory ECG monitors, a mobile cardiac telemetry device, Zio® MCT, is currently in development. Zio MCT will leverage the same patch ECG form factor and end-of-wear ECG review as Zio monitor, but also enables transmission and review of symptomatic or auto-triggered events during the wear period. Zio MCT-specific features, including auto-detection and event transmission during wear will not be enabled nor evaluated as part of this study. However, this assessment of extended wear performance is applicable to both Zio monitor and Zio MCT as the patch devices share the identical electrical, mechanical, and adhesive assembly. The main difference in the patch design is the firmware and the activation of the Bluetooth communication to the Gateway. This is not expected to impact wear duration on Zio MCT as it is not adding weight or changing adhesive area vs Zio Monitor.

The gateway which enables transmissions will not be included in this study.

## 2.4 Number of Participants

[figure not shown]
A total of up to 150 participants will be enrolled in this study. Seventy-five participants have already been enrolled in the first phase of this study which utilized the iRhythm legacy skin preparation process. An additional 75 participants will be enrolled utilizing an updated skin prep process detailed in Section 5.1.

## 2.5 Overall Flow of the Study and Follow-up Schedule

**Figure 1** shows the overall flow of the study. Participants who meet all inclusion and no exclusion criteria are eligible for enrollment into the study. Study visits will be performed in-clinic (Baseline, 21-day and 30-day) and by telephone or video (7- and 14-day).

Participants must read, understand, and sign (by hand) the study Informed Consent Form prior to the initiation of the Baseline assessment visit and start of device wear. Once consented, participants will have a study device applied to their chest by a Study Staff member or be provided a study device to self-apply (i.e., simulated at-home patch application) on-site. Study devices must be applied no later than the expiration date indicated on the kit. Participants will be considered enrolled after they have signed the Informed Consent Form and attempted patch application has occurred. Attempted patch application is defined as the opening of the patch kit and initiation of the shaving step necessary for skin preparation.

During the wear period, participants will be contacted by phone or video call to determine adverse events and remind them of their next visit. Enrolled participants will undergo clinical evaluation at Baseline and 21 days and 30 days after on-site or simulated at-home patch application. They will also be provided a contact number to report any adverse events that occur between planned visits.

**Figure 1: Overall Study Flow****Important Notes:**

1. Participants will be considered enrolled after they have signed the Informed Consent Form and have attempted to apply the patch.

2. Follow-up visits are conducted at the indicated days following application of the patch, whether in clinic or by phone/video call.
3. Early patch detachment and/or completion of the 30-day visit also includes a study completion form.
4. Photos are to be taken at Baseline before and after application, at the 21-day visit of the device, at the 30-day visit of the device both on and off the participant as well as a photo of the skin at the location the patch was worn. Optionally, photos may also be taken at the 7-day and/or 14-day visits if they occur via video call.

### **2.5.1 Study Safety Committee**

A study safety committee will meet as needed to assess any safety events that may occur. The study safety committee meetings will be conducted according to a separate charter. The charter will include meeting scope, roles and activity specifics.

## **3.0 STUDY PERFORMANCE OBJECTIVES AND ADDITIONAL MEASURES**

### **3.1 Wear Time Performance Objective**

Wear duration is defined as the number of days the patch is attached to the participant. Wear duration measurement will start at the time of device application and will end at any of the following events:

- the device is removed at the 30-day follow-up visit, or
- the device fails to adequately adhere to the skin.

All enrolled participants on whom patch application was attempted will be included as part of the mean wear duration analysis. However, participants who discontinue wear of the device for reasons outside of the study protocol, or occurrence of an adverse event not related to the study, will not be counted in the analysis. Full disclosure for reasons of discontinuation will be provided in the study report.

Mean wear duration will be compared to a performance goal of 21 days. The performance objectives will be met if the mean wear duration is greater than 21 days.

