### 1.2 Study Objectives

The objective of the study is to evaluate the wear performance of the Zio monitor device in a representative population over an extended wear period (of up to 30 continuous days) utilizing an updated skin preparation process to demonstrate that the device can be worn with adequate patch adherence and signal quality through 21 days. Assessment of wear performance will include evaluation of the wear duration of the patch and percentage of analyzable electrocardiographic time. Product safety will be assessed by collection of all adverse events.

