### **3.3 Safety Measures**

All enrolled participants on whom patch application was attempted will be included in the safety analysis. The proportion of participants that experience clinically significant skin irritation through 30 days of wear will be assessed.

- Reaction severity will be assessed and reported, as follows [10]:
  - Weak Positive Reaction: Presence of erythema infiltration, discrete papules
  - Strong Positive Reaction: Presence of erythema infiltration, papules, discrete vesicles
  - Extreme Positive Reaction: Presence of bullous or ulcerative reaction, coalescing vesicles

An 'Extreme Positive Reaction' will be considered a clinically significant skin irritation.

Any skin reaction should be reported as an adverse event. Skin reactions are anticipated (see Section 12.2). All adverse events will be reviewed by a physician on the safety committee.

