## 5.2 Patch Wear Period

All consented participants in whom the Zio monitor Patch application is attempted will be considered enrolled in the study. Patch application is considered to have been attempted when the Zio monitor Patch kit is opened and the first step necessary for skin preparation has been initiated. The participant will be instructed to wear the device for as long as possible, up to the 30-day visit.

Study participants will be instructed to press and hold along the edges of the patch if they notice the patch peeling or lifting at the edges during the wear period. If a patch completely detaches from the participant's chest, the patch will not be re-applied. In the case of early patch detachment, the participant should notify study staff of the date and time of detachment, and a study completion visit should be scheduled as soon as possible.

At any time after patch application, if the device is determined to no longer be functioning (for example, if a rapidly blinking orange light is observed), the device will not be replaced. The date and time the determination of function failure will be noted as close to accurate as possible. As a non-functioning device does not present a safety concern, the participant will be asked to continue wearing the non-functioning patch for as long as possible, in order to record wear duration and wear experience data.

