### **5.6 30-Day (±3 days) Participant Follow-up (Visit 5)**

At day 30 following patch application and up to day 33, participants will be asked to return to the clinic and the following activities will be conducted:

- Skin assessment by HCP or designee, including photograph of the area with the device on and also upon device removal
- Adverse Event review
- Zio patch removal and visual inspection, including photograph of front and back of patch
- Patch return to iRhythm Technologies, Inc. for data download and evaluation

Participants who applied the Zio to themselves at the Baseline visit will be asked to remove the patch. They may ask a Study Staff member to provide guidance in the removal process.

Study clinical assessments and activities are summarized in **Table 2**.

Table 2: Clinical Assessment Schedule

Required Assessments to be Collected	Baseline (Visit 1)	7 & 14-Day (Visit 2 & 3)	21-Day (Visit 4)	30-Day (Visit 5)
		±3 days Phone or Video Call only	+3 days	±3 days
Informed Consent 	X	X	-	-
Medical and Cardiac Background/History	X	-	-	-
Fitzpatrick Skin Assessment	X	-	-	-
Skin Condition Assessment  , Including photograph(s)	X	-	X	X
Assessment of Device Adhesion Performance, Including photograph(s)	-	-	X	X
Adverse Events 	X 	X	X	X

1. *Continued Informed Consent will be verified at each post-baseline contact.*
2. *Including chest hair density, as applicable.*
3. *Adverse Events include serious adverse events, all device-related complications, device deficiencies, device malfunctions, procedures and any hospitalizations. If AEs are ongoing at the 30-day visit, the participant should be contacted until resolution, or Day 37, whichever is sooner.*
4. *AEs are only assessed following Informed Consent and participant enrollment into the study.*

The study device will be returned to iRhythm Technologies, Inc. for download and analysis of the ECG signal collected during the wear.

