#### **7.4 Statistical Analyses**

For wear duration performance, mean wear duration, standard deviation and 95% confidence interval will be reported. For analyzable time performance, the mean percent analyzable time, standard deviation, 95% confidence interval, and percentage of patients with analyzable time  $>80\%$  will be reported. Performance objectives will be met if the mean wear duration is greater than 21 days, and percent analyzable time is greater than 80% in 90% of subjects.

For other analyses, mean and standard deviation or median, interquartile range, minimum and maximum will be reported for continuous variables; counts and percentages will be reported for categorical variables.

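### For a patch still adhered at the end, counted wear is the date of an appointment: section 3.1 sets no limit at day 30, and section 5.6 gives two windows for that visit

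*Protocol*

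**What the plan says.** All references are to protocol version 02.

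- **Endpoint.** Section 3.1 counts wear in days attached, from application to one of two end events: the patch fails to adhere, or "the device is removed at the 30-day follow-up visit". It states no maximum.
- **Instruction.** Section 5.2: "The participant will be instructed to wear the device for as long as possible, up to the 30-day visit".
- **Visit window.** The heading of section 5.6 reads "30-Day (±3 days) Participant Follow-up (Visit 5", and Table 2 also has ±3 days. The text under that heading reads "At day 30 following patch application and up to day 33, participants will be asked to return to the clinic". Removal of the patch is a procedure of this visit.
- **Horizon elsewhere.** Section 1.2 describes wear "over an extended wear period (of up to 30 continuous days". Section 2.2 speaks of "participants who will wear the device for up to 30 days, in order to achieve a mean wear time of greater than 21 days". Section 3.3 says that "clinically significant skin irritation through 30 days of wear will be assessed". Section 2.0 and Table 1 describe ECG recording for up to 30 days.
- **Success rule.** Section 7.4: "Performance objectives will be met if the mean wear duration is greater than 21 days". This compares the observed mean with 21, although section 7.2 sizes the study on a one-sample t-test.

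**The concern.** A patch that fails on day 12 has a wear value set by its adhesion. A patch that never fails has a value set by the calendar: attached at a visit on day 32, it counts 32 days. If ±3 is followed, the same patch seen on day 27 counts 27. The endpoint thus mixes adhesion with clinic scheduling, under a visit rule that contradicts itself. Because success is a bare comparison with 21, a shift of less than a day could decide the outcome if the mean lies close to 21.

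**Working it through.** **1. The plan's own figure.** Inputs from section 7.2: mean 24.0, goal 21, SD 9.3, one-sided alpha 0.05, power 80%, one-sample t-test. With difference 24.0 − 21 = 3.0, the noncentral t distribution gives n = 61 with power 80.1%. The stated 61 is reproduced.

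**2. Spread that follows from the text alone.** Text of 5.6: 33 − 30 = 3 days between equally adherent patches. Heading and Table 2: 33 − 27 = 6 days. Both versions allow removal up to day 33, so only days 27 to 29 are in dispute.

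**3. Shift of the mean relative to a 30-day mean.** This needs two assumptions that the protocol does not supply: the share p still adhered at day 30, and when visits take place. Approximately, shift = p × average visit delay after day 30. Three models of detachment were matched to a given 30-day mean m:

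- (a) Two-point with SD 9.3: p = r/(1 + r), r = 9.3²/(30 − m)². For m = 21, r = 86.49/81 = 1.068 and p = 51.6%. For m = 24, r = 86.49/36 = 2.40 and p = 70.6%.
- (b) Weibull with SD 9.3: p = 36.7% (m = 21) and 62.0% (m = 24).
- (c) Exponential: p = 46.7% and 62.9%.

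With visits spread evenly over days 30 to 33 the average delay is 1.5 days. In model (c) at m = 21 this gives about 0.467 × 1.5 = 0.70; simulation gives 0.68. Simulated means:

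| 30-day mean | visits on days 30–33 (a/b/c) | visits on days 27–33 (a/b/c) |
|---|---|---|
| 21 | 21.79 / 21.54 / 21.68 | 21.01 / 20.99 / 20.98 |
| 24 | 25.06 / 24.93 / 24.93 | 24.00 / 24.00 / 23.99 |

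An evenly used ±3 window therefore produces no net shift.

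**4. Chance that the observed mean exceeds 21** (n = 75, 20,000 simulated trials per cell, range over the three models):

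| 30-day mean | all removed on day 30 | visits on days 30–33 |
|---|---|---|
| 19.5 | 8–11% | 17–24% |
| 20 | 18–21% | 31–39% |
| 21 | 50–51% | 68–75% |
| 22 | 80–83% | 92–94% |
| 22.5 | 90–92% | 97–98% |
| 23 | 96–97% | 99% |
| 24 | 99.6% | 99.9–100% |

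On a grid of 0.5 days, the gain is at least 5 percentage points in all three models only from 19.5 to 22.5. Visit timing drives it: in the exponential model at 21, visits over days 30–31 give about 58%, against about 70% over days 30–33.

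**5. The literal quantity.** Set the mean days attached up to a visit on days 30–33 to exactly 21. The observed mean then exceeds 21 in 50–51% of trials, and a one-sided 0.05 t-test rejects in 5.7% (exponential and Weibull models, 40,000 trials). This corresponds to a 30-day mean of 20.4 to 20.5.

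**6. What a cap does.** On the days 30–33 schedule, min(days, 30) returns the day-30 results exactly. If removals spread over days 27–33, the late half is cut and the early half is not restored. The loss is about p × 0.5 × 1.5 = 0.75p. In model (a) at m = 24 that is 0.75 × 0.706 = 0.53, so the mean falls from 24.0 to about 23.5. At m = 21 it falls to 20.6–20.7.

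**The case against.** The strongest reply is that 3.1 is a complete rule: a patch attached for 32 days was worn for 32 days, and truncation is a data-handling choice that a statistical analysis plan, not shown here, may make. Much of this stands. The missing limit is not itself a contradiction, and the shift in step 3 exists only against a 30-day mean that the protocol implies without defining. It is also true that the upper limit of the visit, day 33, is the same in both versions, that early removal can only lower the recorded wear, and that the notes to Figure 1 place visits on the indicated days. What remains is that the protocol itself fixes the end event as a visit and prints two windows for that visit.

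Three stronger readings are tempting, and the documents support none of them.

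- *Late visits inflate the false-positive rate.* Step 5 shows that they do not on the quantity that 3.1 defines.
- *The planning values or N = 61 are wrong.* Section 7.2 does not say whether the prior 24.9 ± 9.3 was limited at 30 days, and the SD cannot tell. The largest possible SD at that mean is √(24.9 × 5.1) = 11.3 with a limit at 30 and √(24.9 × 8.1) = 14.2 with a limit at 33; 9.3 fits both.
- *Power could fall to 39% or rise to 96%.* With half the patches still adhered and n = 61, the t-test has this power only if every visit falls on day 27 or every visit on day 33. These are outer bounds, and they concern the t-test rather than the written comparison with 21.

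**Conclusion.** The point holds as a minor defect. Without any assumption: the wear value of every patch still adhered at the end is an appointment date, section 5.6 contradicts itself on when that appointment may fall, and equally adherent patches can differ by 3 or 6 days.

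The rest is conditional. If a 30-day mean is what is intended, if visits spread evenly over days 30–33, and if 37–71% of patches are still adhered at day 30, the mean rises by about 0.5 to 0.8 days at a 30-day mean of 21 and by 0.9 to 1.1 at 24. That could affect the result only for a 30-day mean of roughly 19.5 to 22.5. At the planned 24 it does not change the conclusion.

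**What to change.** 1. Reconcile the Visit 5 window across the heading and text of section 5.6 and Table 2. Which window applies is for the sponsor to settle.
2. State in section 3.1 that analysed wear is min(days attached, 30), in line with the wear period of up to 30 days in sections 1.2 and 2.2.
3. Only if the reconciled window still allows removal before day 30, add a sensitivity analysis for adhered patches removed early, because the cap alone would then lower the mean (step 6). One option is to treat such removals as censored and report the mean restricted to day 30. This is a different estimator from the simple mean, and it needs extrapolation if no patch is observed to day 30.

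Prespecify this for Phase 2. For Phase 1, apply it to the recorded removal dates and disclose that the rule was set after those visits fell due. Section 5.1 has enrolment complete by 28 February 2025, so the last Visit 5 fell due by 2 April 2025 (28 February + 33 days), 21 days before version 02 was released on 23 April 2025. The documents do not show whether Phase 1 results were known by then.

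The cost is one sentence in 3.1 and a correction in 5.6 and Table 2. No new data are needed and N = 61 is unaffected. The downside is a slightly lower reported mean where visits ran late.

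### A mean wear above 21 days, with wear counted to the 30-day visit, does not by itself show that the patch can be worn through 21 days

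*Protocol*

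**What the plan says.** Protocol version 02, section 1.2, gives the aim as to "demonstrate that the device can be worn with adequate patch adherence and signal quality through 21 days". Section 3.1 turns adherence into a mean: "Mean wear duration will be compared to a performance goal of 21 days". Success is then defined as follows: "The performance objectives will be met if the mean wear duration is greater than 21 days". Section 7.4 repeats the rule and adds the signal criterion, whose last figure is a share of participants: "Performance objectives will be met if the mean wear duration is greater than 21 days, and percent analyzable time is greater than 80% in 90%". As wear duration outputs, section 7.4 names three: the mean, the standard deviation and a 95% confidence interval.

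The wear count has no stop at day 21. Under section 3.1 it ends when the patch fails to adhere or when "the device is removed at the 30-day follow-up visit, or". Section 5.2 adds: "The participant will be instructed to wear the device for as long as possible, up to the 30-day visit". Section 5.6 places that visit "At day 30 following patch application and up to day 33".

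Section 7.2 bases the sample size on a one-sample t-test at one-sided 0.05, with a mean of 24.0 days, an SD of 9.3 days and 80% power.

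**The concern.** The objective asks whether patches stay on through day 21. The criterion asks whether average wear exceeds 21 days when each participant can contribute 30 days or more. A participant who reaches day 30 brings nine days above the goal, and these cancel nine days lost by someone whose patch came off early. The study could therefore declare its adherence objective met although a sizeable minority of patches had come off well before day 21, and the protocol's named wear outputs would not show how many.

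The signal criterion does not protect against this. Section 3.2 defines analyzable time as a percentage of the time the device is worn, so a patch lost in the first week can still pass. The protocol does use a per-subject rule for signal quality (above 80% in 90% of subjects), but it has none for adherence.

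**Working it through.** **1. The plan's own figure.** Inputs from section 7.2: difference 24.0 − 21 = 3.0 days, SD 9.3, one-sample t-test, one-sided alpha 0.05, power 80%. With the noncentral t distribution, the smallest n reaching 80% is 61 (power 80.1%). The stated 61 is correct for a test of the mean.

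**2. Early loss that the point-estimate rule tolerates.** Assume a share p detaches at day x and the rest are worn to day C. Then mean = C − p(C − x), and the mean exceeds 21 when p < (C − 21)/(C − x).
- x = 7, C = 30: p < 9/23 = 39.1%.
- In whole patches with n = 75, 29 off at day 7 and 46 worn to day 30 give (29×7 + 46×30)/75 = 1583/75 = 21.1 days, so the goal is met. With 30 off, the mean is (210 + 1350)/75 = 20.8 days, and it is not.

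**3. The same case under the planned t-test** (one-sided 0.05, n = 75, critical t = 1.666).
- 22 off at day 7: mean 23.25, SD 10.54, t = 2.25/(10.54/√75) = 1.85, which passes.
- 23 off at day 7: mean 22.95, SD 10.68, t = 1.58, which fails.
- The limit is 22/75 = 29%. With n = 61 it is 17/61 = 28%.
- If everyone else stays on to day 33, the limits become 27/75 = 36% and 21/61 = 34%.

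**4. What the planning values imply without assuming a shape.** For any wear X between 0 and 30 days, (X − 21)(X − 30)/(21×30) is at most 1 when X < 21 and at most 0 when X is between 21 and 30. Its expectation is therefore a lower bound on the probability that X < 21.
- E(X²) = 24.0² + 9.3² = 576 + 86.49 = 662.49.
- Bound = (662.49 − 51×24.0 + 630)/630 = 68.49/630 = 10.9%.
- With a cap of 33 days the same formula gives 8.6%.

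**5. What they imply under assumed shapes, cap 30.** The protocol gives only a mean and an SD, so these shapes are assumptions.

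| Assumed shape | Short of day 21 |
|---|---|
| Scaled beta | 25% |
| Censored normal | 27% |
| Constant detachment hazard (mean 24.0 only) | 28% |
| Two-point, matched to mean and SD | 29% |

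The two-point row puts early detachment at day 24 − 86.49/6 = 9.6, with share 6/(30 − 9.585) = 29%. Mixtures of a point mass at day 30 and a scaled beta give 25% to 30%.

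**6. Chance of passing the t-test with such a pattern.** With 30% off at day 10 and 70% worn to day 30, the true mean is 0.3×10 + 0.7×30 = 24.0. By simulation the test succeeds about 82% of the time at n = 61 and 84% at n = 75.

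**The case against.** The strongest defence is that the criterion is open and consistent. Sections 2.0, 2.2, 3.1 and 7.4 all define success on mean wear, and section 2.2 gives a mean above 21 days as the aim. The objective in section 1.2 can be read as a statement of capability that the protocol then makes operational as a mean, and nowhere does it promise that a given share of participants will reach day 21. A descriptive proportion could also appear in a statistical analysis plan that is not shown. This shows that the mean is a legitimate goal for a claim about mean wear. It does not remove the mismatch, because the protocol itself fixes both the objective and the success rule, and the rule answers a different question.

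It is also fair to say that the plan holds some day-21 information. Device Functionality (section 3.4) is the proportion of devices recording continuous ECG for 21 days. Since a detached patch cannot do that, it is a lower bound on attachment. Table 2 schedules an adhesion assessment at the 21-day visit, and section 5.2 asks for the date and time of detachment. But Device Functionality mixes detachment with recording failure and carries no goal, and the protocol names no summary of the adhesion data.

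A reader might infer stronger claims that the documents do not support:
- That 39% early loss would be accepted whatever the test. This holds only if success is judged on the point estimate, which sections 3.1 and 7.4 allow. Under the t-test of section 7.2 the limit is 29%.
- That the limit is 46%, from (33 − 21)/(33 − 7). This is again a point-estimate limit, and it needs every remaining participant to attend on the last permitted day. The section 5.6 heading gives the visit a ±3-day window, so some removals may come before day 30.
- That the planning values show 25% to 30% off by day 21. That range depends on the assumed shape. The mean and SD alone require only about 11%.

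**Conclusion.** The point stands as a mismatch between objective and success criterion. It is not an error in the sample size or in the mean analysis. A met mean goal supports the statement that mean wear exceeds 21 days. It does not by itself support wear through 21 days.

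In the two-point illustration, the tolerated loss at day 7 is 29 of 75 on the point estimate and 22 of 75 under the planned test. That pattern (day 7 or day 30) is an assumption chosen to show the mechanism, not a forecast. The 11% shortfall rests only on the planning mean and SD and a 30-day cap. The 25% to 30% range rests also on assumed distributions. The matter should be corrected, since the rule as written can be met by data that do not show what the objective states.

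**What to change.** Keep the mean goal and the sample size. In sections 3.1 and 7.4:
- Add the proportion of participants with the patch still attached at day 21, with a 95% confidence interval, as a Kaplan-Meier estimate or a simple proportion, reported beside the mean for each phase.
- State that meeting the mean goal supports a conclusion about mean wear only, and that any statement about wear through 21 days rests on the reported day-21 proportion.

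The data are already being collected: detachment dates and times, and the adhesion assessment at the 21-day visit. The cost is one further analysis and some wording, with no change to enrollment or visits. As a guide to precision, if 52 to 56 of 75 patches were attached at day 21, the exact 95% intervals would together span about 58% to 84%. The downside for the sponsor is that the day-21 proportion will look less favourable than the mean.
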